8.4.1 Primary Endpoint and Associated Hypotheses

No formal hypotheses are specified for the primary endpoint of this study.

The primary performance endpoint in this study is the number and percentage of vessels where hemostasis (\leq Grade 3) is achieved using the ENSEAL X1 device. The hemostasis grading scale is defined as:

- Grade 1: no bleeding at transection site;
- Grade 2: minor bleeding at transection site, no intervention needed;
- Grade 3: minor bleeding at transection site, mild intervention needed, use of compression, basic energy devices (monopolar and/or bipolar device), and/or touch-ups with ENSEAL X1.
- Grade 4: significant bleeding (e.g., pulsatile blood flow, venous pooling) requiring intervention such as extensive coagulation or use of additional hemostatic measures (e.g., hemoclips, staples, sutures, fibrin sealants, other advanced energy products).

The primary performance endpoint will be summarized at the vessel transection level as multiple vessel transections per subject are expected; that is, the denominator for the primary endpoint will be the total number of vessel transections and the numerator will be the number of vessel transections where hemostasis (\leq Grade 3) is achieved. An exact 95% confidence interval using the Clopper-Pearson method will be estimated. The statistics for the primary performance endpoint will be presented by procedure group and in total.

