8.8 Sensitivity Analyses

The analysis of the primary performance endpoint described above in Section 8.4.1 makes the assumption of independence of vessel transections within a subject in estimation of variance for the confidence interval calculation. If the percentage of subjects with two or more vessel transections exceeds 10% a sensitivity analysis will be performed to account for the potential dependence among vessel transections within a subject. The 95% confidence interval will be estimated using a bootstrap approach. If the percentage of subjects with two or more vessel transections is less than 10% the bias due to assuming independence is expected to be small, and no sensitivity analysis will be conducted.

Bootstrap process:

For each subject, the outcome of each activation will be represented by a vector of 1's (indicating a score of \leq Grade 3 hemostasis) and 0's (indicating a score of Grade 4 hemostasis). This vector will be re-sampled with replacement to generate a bootstrap sampled vector of observations for each subject. Then, the proportion of observations scored as \leq Grade 3 hemostasis for the bootstrap sample will be calculated. This process will then be repeated a minimum of 5000 times to generate a sampling distribution for the proportion of activations achieving \leq Grade 3 hemostasis. The mean of this sampling distribution will be provided as the point estimate of the proportion of activations achieving \leq Grade 3 hemostasis and the 95% confidence interval will be estimated by the lower 0.025 and upper 0.975 percentiles of this sampling distribution.

The table below demonstrates 1 iteration of this bootstrap process.

Subject ID	Observed Data Vector	Bootstrap Sampled Vector
1	(1, 1, 0, 1, 1)	(1, 0, 1, 0, 1)
2	(1, 1, 1)	(1, 1, 1)
3	(1, 0, 1, 1)	(0, 1, 1, 1)
4	(1, 1, 0, 1, 1)	(1, 1, 1, 1, 1)
5	(1, 1)	(1, 1)
...
...
N	(0, 1, 1, 0, 1)	(1, 0, 1, 1, 1)
Summary		Count the number of 1's/Total number of 1's and 0's

The above re-sampling process will then be repeated a minimum of 5000 times to estimate the sampling distribution.

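### The reported primary 95% interval treats vessels from the same subject as independent and can under-cover when several are transected per subject; the conditional bootstrap row does not repair it

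*SAP*

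**What the plan says.** SAP 8.4.1 makes the vessel the unit of analysis: "The primary performance endpoint will be summarized at the vessel transection level as multiple vessel transections per subject are expected", and "the denominator for the primary endpoint will be the total number of vessel transections". It then adds: "An exact 95% confidence interval using the Clopper-Pearson method will be estimated", by procedure group and in total. Protocol 5.9.4 and the synopsis likewise call for an exact 95% interval on vessels.

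SAP 8.8 is open about what this implies. It says that the primary analysis "makes the assumption of independence of vessel transections within a subject in estimation of variance for the confidence interval calculation". The remedy is conditional: "If the percentage of subjects with two or more vessel transections exceeds 10% a sensitivity analysis will be performed", and its purpose is "to account for the potential dependence among vessel transections within a subject". Below the threshold, "the bias due to assuming independence is expected to be small, and no sensitivity analysis will be conducted".

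The bootstrap in SAP 8.8 redraws each subject's own vector of outcomes with replacement. Every subject appears in every bootstrap sample; subjects themselves are not resampled. SAP Table 9 prints the bootstrap interval under the exact one and labels it a sensitivity analysis.

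**The concern.** A Clopper-Pearson interval is exact for independent binomial trials. Vessels in one patient share tissue quality, disease, medication and one operation, so positive correlation within a subject is plausible. If it is present, the vessel count overstates the information, and the interval is too narrow by an amount that grows with the number of vessels per subject.

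The interval matters because the study tests no hypothesis and sets no performance threshold. Uncertainty about the primary endpoint is conveyed by this interval and, if triggered, the bootstrap row. The stated objective is to demonstrate acceptable performance, and SAP 8.4 foresees comparing results with the literature. An interval labelled exact would probably be read at face value.

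Two features keep the allowance in SAP 8.8 from settling the matter. The headline interval stays the same whatever the sensitivity row shows. And the trigger counts subjects with two or more vessels but ignores how many vessels those subjects have, which is what drives the loss of information.

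**Working it through.** **1. The plan's own figures.** The documents state no precision or expected rate for the primary endpoint. The two figures in SAP 7 concern safety and reproduce: 1 − 0.98^105 = 0.880, and the two-sided exact upper limit for 0/105 is 1 − 0.025^(1/105) = 3.45%, below the stated 3.5%. Both count subjects, so within-subject dependence does not arise there.

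**2. Inputs.** From the documents: 105 subjects in total, 35 per group (the planned minima). Assumed, because the documents are silent: beta-binomial outcomes, a true rate of 95% or 98%, 2, 3 or 5 vessels per subject (m, equal across subjects), and ICC from 0 to 0.3.

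**3. Width.** Design effect = 1 + (m − 1) × ICC; effective size = vessels / design effect.

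- m = 3, ICC 0.2, rate 95%: 315 vessels, design effect 1 + 2 × 0.2 = 1.4, effective size 315 / 1.4 = 225. The interval goes from 92.0–97.1% to 91.3–97.5%, about 1.2 times as wide.
- m = 5, ICC 0.3, rate 95%: 525 vessels, design effect 1 + 4 × 0.3 = 2.2, effective size 239. The interval goes from 92.8–96.7% to 91.4–97.4%, about 1.5 times as wide.

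**4. Coverage of the planned interval** (simulated, 20,000 runs per cell, nominal 95%):

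| Subjects | Rate | Vessels each | ICC 0 | 0.1 | 0.2 | 0.3 |
|---|---|---|---|---|---|---|
| 105 | 95% | 2 | 96.3 | 95.1 | 94.1 | 93.2 |
| 105 | 95% | 3 | 96.1 | 94.0 | 92.2 | 89.7 |
| 105 | 95% | 5 | 95.5 | 91.1 | 86.6 | 82.7 |
| 105 | 98% | 2 | 97.4 | 96.9 | 96.0 | 94.9 |
| 105 | 98% | 3 | 97.5 | 96.3 | 94.3 | 92.4 |
| 105 | 98% | 5 | 95.7 | 91.9 | 87.4 | 83.0 |
| 35 | 95% | 2 | 97.6 | 97.0 | 96.4 | 95.8 |
| 35 | 95% | 3 | 98.0 | 96.6 | 95.1 | 94.1 |
| 35 | 95% | 5 | 96.3 | 92.5 | 87.7 | 83.4 |
| 35 | 98% | 2 | 98.8 | 98.1 | 97.8 | 97.2 |
| 35 | 98% | 3 | 98.1 | 96.8 | 95.8 | 95.0 |
| 35 | 98% | 5 | 99.0 | 97.5 | 95.9 | 94.3 |

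Equal vessel counts are the favourable case. With 53 subjects at 1 vessel, 26 at 3 and 26 at 7, the mean is 313/105 = 3.0, but Σm²/Σm = 1561/313 = 5.0. Coverage at a 95% rate is then about 92/87/83% for ICC 0.1/0.2/0.3, close to the five-vessel row.

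**5. The trigger.** For unequal counts, design effect = 1 + (Σm²/Σm − 1) × ICC. Take 10 of 105 subjects (9.5%, so no sensitivity analysis) with 8 vessels each and 95 with one. Σm = 80 + 95 = 175, Σm² = 640 + 95 = 735, and the ratio is 4.2. The design effect is 1 + 3.2 × ICC, or 1.32 to 1.96 for ICC 0.1 to 0.3. Coverage is about 93/90/87% at a 95% rate, but about 98/96/95% at a 98% rate.

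**6. The bootstrap row.** Resampling within a subject holds that subject's expected rate at its observed value, so between-subject variation drops out. A subject with one vessel, or with identical outcomes, contributes no variance. At 105 subjects, a 95% rate, 3 vessels and ICC 0.2 (400 runs of 1,000 resamples; simulation error about 1 to 2.5 points):

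| Interval | Mean width (points) | Coverage |
|---|---|---|
| SAP 8.8 bootstrap | 3.4 | about 77% |
| Vessel-level Clopper-Pearson | 5.1 | about 92% |
| Bootstrap resampling subjects | 5.6 | about 94% |

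The sensitivity row is narrower than the interval it is meant to check. Even with no correlation, at 2 vessels each, it covers about 85% (95% rate) or 73% (98% rate).

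**7. The alternative.** Clopper-Pearson on a subject-clustered effective size (defined with the fix) covered 95–96% pooled at a 95% rate and 94–96% at a 98% rate. For groups of 35 it covered 92–99%, lowest with five vessels each, ICC 0.3 and a 95% rate.

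**The case against.** The best defence is that nothing is hidden. SAP 8.8 states the assumption and plans a second interval, and Table 9 prints both together. With a sound second row, the dispute would shrink to which row is called primary. That is fair, but the row as specified is not sound, so the reader would have no valid clustered interval.

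Three stronger readings are tempting, and the documents do not support them.

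- A reader might infer that the sponsor expects dependence and ignores it. The SAP expects multiple transections; it treats dependence only as a possibility.
- A reader might call this the trial's only inferential statement. Protocol 5.9.1 also plans intervals for procedure-related variables, Table 9 has two interval rows, and no decision rule rests on either. SAP 8.4 speaks of comparing results with the literature, not of comparing this interval.
- A reader might conclude that the interval certainly covers less than 95%. Clopper-Pearson is conservative, and with two vessels per subject, low correlation, or a group of 35 at a 98% rate, coverage stays near or above nominal. Success includes Grade 3, so rates above 95% are plausible.

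The trigger example is also a special case: about 90% of its subjects have one vessel. If multiple vessels are common, as SAP 8.4.1 expects, the trigger fires, but what it starts is the faulty bootstrap.

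Two limits of the alternative stand. With no Grade 4 vessel, its variance estimate is zero and it needs a fallback; at a 98% rate this happens in roughly 15% to 30% of groups of 35 with two or three vessels each and ICC 0.1 to 0.3. And surgeon or generator effects shared across subjects are not captured by clustering on subject.

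**Conclusion.** The point holds in conditional form. The reported primary interval assumes independence among vessels that the plan expects to come several to a subject, and the only planned allowance neither replaces it nor captures between-subject variation. With positive correlation and several vessels per subject, the interval can cover less than its stated 95%.

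The shortfall is negligible with two vessels per subject at a 98% rate. In the pooled analysis at a 95% rate it is about 1 to 5 points with three vessels and about 4 to 12 points with five, for ICC 0.1 to 0.3. Rates, vessel counts, ICC and the beta-binomial form are all assumptions. Confidence is high that the assumption is built into the headline interval and that the bootstrap fails to relax it; how much coverage is lost will depend on the data.

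**What to change.** In SAP 8.4.1 and Table 9, make the reported interval subject-clustered, by procedure group and in total:

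- Let p be the vessel-level proportion, m_i the vessels and y_i the successes in subject i, and k the number of subjects. Compute v = [k/(k − 1)] × Σ(y_i − m_i p)² / (Σm_i)².
- Apply Clopper-Pearson to the effective size p(1 − p)/v, capped at the number of vessels (the Korn-Graubard approach).
- State that when no Grade 4 vessel occurs, so that v = 0, the effective size equals the number of vessels.
- Keep the vessel-level Clopper-Pearson row as supportive, labelled as assuming independence.
- Delete the 10% trigger in SAP 8.8.
- Put matching wording in Protocol 5.9.4 and the synopsis, which now specify an exact interval.

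The cost is a SAP amendment (SAP 8.1 exempts only changes that leave the methodology alone), a protocol wording change and a few lines of SAS. No new data are needed. The reported interval becomes somewhat wider. Slight under-coverage, to about 92%, remains in groups of 35 with many vessels per subject and high correlation.

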8.4.2 Secondary Endpoints and Associated Hypotheses

No formal hypotheses are specified for the secondary endpoints of this study.

Counts and percentages will be provided for the following secondary endpoints:

- Satisfaction scores in 5-point scale for the following tasks completed by the ENSEAL X1 device:
 - Adhesion removal or division
 - Lymphatics bundles division
 - Tissue bundles division
 - Tissue grasping
 - Tissue cutting
 - Tissue dissection

- Hemostasis grading scale (1-4) for all vessel transected
- Type, name, and number of additional hemostasis measures required to achieve hemostasis for Grade 4 vessel transections by:
 - Name of vessel transected
 - Number of additional hemostatic measure(s) used to obtain hemostasis
 - Type of additional hemostatic measure(s) used to obtain hemostasis

8.4.3 Additional Endpoints

Summary statistics will be provided for the following endpoints:

- Procedure duration
- Use of any other energy device (basic [monopolar and traditional bipolar], advanced bipolar, ultrasonic) in primary procedure (type, name, and number of device and reason for use)
- Surgeon questionnaire administered once per investigator
- Generator questionnaire after each procedure for each GEN11 used
- Surgical procedure conducted
- Hospital stay duration
- Name and number of vessels that were transected
- Surgeon determination of diameter size range (< 3 mm, 3 to 5 mm, and > 5 to 7 mm)
- Occurrence and location of cancer and occurrence of pre-surgical radiation/chemotherapy within 90 days prior to surgery
- Occurrence of vessel skeletonization
- Presence of inflamed tissue, calcified tissues/vessels, atherosclerotic tissue, fibrotic tissue, or presence of adhesions intraoperatively
- Volume of estimated intra-operative blood loss
- Occurrence of blood transfusion, total required units of blood, and time point of transfusion
- Type of additional mild interventions (use of compression, basic energy devices [monopolar and/or bipolar] and/or touch-ups with ENSEAL X1) required to achieve hemostasis for Grade 3 vessel transections including number of times when ENSEAL X1 touch-ups were used
- Protocol deviation classified as minor or major, rationale for deviation, type of protocol deviation, and outcome of protocol deviation in terms of subject's discontinuation of study

8.5 Safety Analyses

The primary safety endpoint in this study is the occurrence of device-related AEs. As per the study protocol, device-related AEs are those identified as having a relationship of possibly, probably, or causally. AEs unrelated to the study device are recorded as 'not related' on the CRF. Both device-related and procedure-related AEs reported during the study will be coded to MedDRA. All reported AEs will be summarized by MedDRA system organ class and preferred term by the entire pooled subjects. Separate summaries will be provided for device-related and procedure-related AEs. Serious AEs will be summarized in a similar manner. The safety endpoints will be summarized by procedure group and on the entire pooled set of subjects. All reported adverse events will be listed.

Listings will also be provided for blood transfusion details, concomitant procedures, and concomitant medications.

Safety endpoints are as follows:

- All AEs
- Serious AEs
- All AEs related to the study device
- Serious AEs related to the study device
- All AEs related to the study procedure
- Serious AEs related to the study procedure

8.6 Plans for Interim Analysis

No interim analyses are planned for this study.

8.7 Handling of Missing Data

All summaries will be performed for enrolled subjects only and with observed data. There will be no imputation of data for early terminated subjects or for missing data within the database.

8.8 Sensitivity Analyses

The analysis of the primary performance endpoint described above in Section 8.4.1 makes the assumption of independence of vessel transections within a subject in estimation of variance for the confidence interval calculation. If the percentage of subjects with two or more vessel transections exceeds 10% a sensitivity analysis will be performed to account for the potential dependence among vessel transections within a subject. The 95% confidence interval will be estimated using a bootstrap approach. If the percentage of subjects with two or more vessel transections is less than 10% the bias due to assuming independence is expected to be small, and no sensitivity analysis will be conducted.

Bootstrap process:

For each subject, the outcome of each activation will be represented by a vector of 1's (indicating a score of \leq Grade 3 hemostasis) and 0's (indicating a score of Grade 4 hemostasis). This vector will be re-sampled with replacement to generate a bootstrap sampled vector of observations for each subject. Then, the proportion of observations scored as \leq Grade 3 hemostasis for the bootstrap sample will be calculated. This process will then be repeated a minimum of 5000 times to generate a sampling distribution for the proportion of activations achieving \leq Grade 3 hemostasis. The mean of this sampling distribution will be provided as the point estimate of the proportion of activations achieving \leq Grade 3 hemostasis and the 95% confidence interval will be estimated by the lower 0.025 and upper 0.975 percentiles of this sampling distribution.

The table below demonstrates 1 iteration of this bootstrap process.

Subject ID	Observed Data Vector	Bootstrap Sampled Vector
1	(1, 1, 0, 1, 1)	(1, 0, 1, 0, 1)
2	(1, 1, 1)	(1, 1, 1)
3	(1, 0, 1, 1)	(0, 1, 1, 1)
4	(1, 1, 0, 1, 1)	(1, 1, 1, 1, 1)
5	(1, 1)	(1, 1)
...
...
N	(0, 1, 1, 0, 1)	(1, 0, 1, 1, 1)
Summary		Count the number of 1's/Total number of 1's and 0's

The above re-sampling process will then be repeated a minimum of 5000 times to estimate the sampling distribution.

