5 Levels of Significance

No hypotheses are specified for this study and no p-values are being calculated, therefore no level of significance is specified. All estimation of endpoints will be performed using 95% confidence intervals.

6 Analysis Sets

The summary of all performance and safety endpoints will be performed on the set of subjects in whom the ENSEAL X1 device is utilized during the surgical procedure. This will be labeled the ENSEAL Analysis Set. This set of subjects will be identified by having at least one entry in the “Vessel Transected” eCRF or by having answered “Yes” to the question “Was ENSEAL X1 used for tissue cutting or dissection?” on the “ENSEAL X1 Usage” eCRF. The summary of all primary and secondary performance endpoints will be performed by procedure group (thoracic, urologic, and ENT) and on the entire pooled set of subjects. The safety endpoints will be summarized by procedure group and for the entire pooled set of subjects.

7 Sample Size Justification

A sample size of 105 to 120 treated subjects is planned for enrollment in this study. No formal hypothesis is being tested in this study; thus, the sample size was not statistically sized, but rather is considered sufficient for a descriptive summary of performance endpoints within each procedure group. It is expected that at least 1 vessel will be transected within each procedure, providing an expected minimum of at least 35 transections within each procedure group for a total of at least 105 transections.

From a safety perspective on the pooled analysis of 105 subjects and in consideration of rare AEs that may occur (e.g., bleeding requiring blood product transfusion), for an event that has an incidence rate of, for example, 2%, then in a sample of 105 subjects, the probability of observing at least 1 event is 88.0% under a binomial probability model. Thus, this sample size provides a high probability of observing an AE if they do occur and provides reasonable assurance to conclude that

the likelihood of such AEs is less than 3.5% if they do not occur based on the upper limit of an exact 95% confidence interval when 0 events out of 105 subjects are observed.

8 Analyses to be Conducted

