Very satisfied	xx (xx.x)	xx (xx.x)	xx (xx.x)	xx (xx.x)

Was there use of any other energy device (monopolar, traditional bipolar, advanced bipolar, ultrasonic) during the primary procedure?

Yes	xx (xx.x)	xx (xx.x)	xx (xx.x)	xx (xx.x)
No	xx (xx.x)	xx (xx.x)	xx (xx.x)	xx (xx.x)

Type of any other energy device used

None	xx (xx.x)	xx (xx.x)	xx (xx.x)	xx (xx.x)
Monopolar	xx (xx.x)	xx (xx.x)	xx (xx.x)	xx (xx.x)
Traditional bipolar	xx (xx.x)	xx (xx.x)	xx (xx.x)	xx (xx.x)
Advanced bipolar	xx (xx.x)	xx (xx.x)	xx (xx.x)	xx (xx.x)

Ultrasonic

xx (xx.x)

xx (xx.x)

xx (xx.x)

xx (xx.x)

¹ Denominator represents the corresponding usage of ENSEAL X1

Table 9
 Vessel Transection Summary – Original Procedure
 ENSEAL Analysis Set

Characteristic	Thoracic (n = xx)	Urologic (n = xx)	ENT (n = xx)	Total (n = xx)
Total Number of Vessels Transected	xx	xx	xx	xx
Hemostasis Grading Scale				
Grade 1	xx (xx.x)	xx (xx.x)	xx (xx.x)	xx (xx.x)
Grade 2	xx (xx.x)	xx (xx.x)	xx (xx.x)	xx (xx.x)
Grade 3	xx (xx.x)	xx (xx.x)	xx (xx.x)	xx (xx.x)
Grade 4	xx (xx.x)	xx (xx.x)	xx (xx.x)	xx (xx.x)
Hemostasis Achieved (Grade 3 or lower)				
Yes	xx (xx.x)	xx (xx.x)	xx (xx.x)	xx (xx.x)
95% Confidence Interval (exact method)	(xx.x, xx.x)	(xx.x, xx.x)	(xx.x, xx.x)	(xx.x, xx.x)
95% Confidence Interval (bootstrap method – sensitivity analysis)	(xx.x, xx.x)	(xx.x, xx.x)	(xx.x, xx.x)	(xx.x, xx.x)
Surgeon determination of diameter size range				
< 3 mm	xx (xx.x)	xx (xx.x)	xx (xx.x)	xx (xx.x)
3 to 5 mm	xx (xx.x)	xx (xx.x)	xx (xx.x)	xx (xx.x)
> 5 to 7 mm	xx (xx.x)	xx (xx.x)	xx (xx.x)	xx (xx.x)
Was an image captured with the vessel in an open jaw of the ENSEAL XI device perpendicular to the vessel?				
Yes	xx (xx.x)	xx (xx.x)	xx (xx.x)	xx (xx.x)
No	xx (xx.x)	xx (xx.x)	xx (xx.x)	xx (xx.x)
Determination of vessel diameter size from image				
N	xx	xx	xx	xx
Mean (SD)	xx.x (xx.x)	xx.x (xx.x)	xx.x (xx.x)	xx.x (xx.x)
Median (Min, Max)	xx.x (xx, xx)	xx.x (xx, xx)	xx.x (xx, xx)	xx.x (xx, xx)
Name of Vessel Transected				
Name 1	xx (xx.x)	xx (xx.x)	xx (xx.x)	xx (xx.x)
Name 2	xx (xx.x)	xx (xx.x)	xx (xx.x)	xx (xx.x)
Name 3	xx (xx.x)	xx (xx.x)	xx (xx.x)	xx (xx.x)
...				
Grade 3 Vessels Using Compression [3]	xx (xx.x)	xx (xx.x)	xx (xx.x)	xx (xx.x)
Grade 3 Vessels Using Monopolar Touch-up [3]	xx (xx.x)	xx (xx.x)	xx (xx.x)	xx (xx.x)

Number of Touch-up of Grade 3 Vessels Using Monopolar Device [3]

N	xx	xx	xx	xx
Mean (SD)	xx.x (xx.x)	xx.x (xx.x)	xx.x (xx.x)	xx.x (xx.x)

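### The SAP 8.8 bootstrap redraws vessels inside each subject instead of redrawing subjects, so its interval narrows as within-subject dependence grows

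*SAP*

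**What the plan says.** The primary endpoint is analysed per vessel. SAP 8.4.1 states: "The primary performance endpoint will be summarized at the vessel transection level as multiple vessel transections per subject are expected". Its interval is specified there as follows: "An exact 95% confidence interval using the Clopper-Pearson method will be estimated".

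SAP 8.8 acknowledges that this interval assumes independent transections. If more than 10% of subjects have two or more transections, "a sensitivity analysis will be performed to account for the potential dependence among vessel transections within a subject". The mechanism is a bootstrap on each subject's vector of 1's (Grade 3 or lower) and 0's (Grade 4): "This vector will be re-sampled with replacement to generate a bootstrap sampled vector of observations for each subject". The redrawn vectors of all subjects are pooled into one proportion. This is repeated at least 5000 times, and the 2.5th and 97.5th percentiles form the interval.

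A worked table follows ("The table below demonstrates 1 iteration of this bootstrap process"). Each subject appears once, in the same order and with its vector length unchanged. The all-1 vectors of subjects 2 and 5 return all 1's.

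Table 9 in the SAP Appendix reports this interval directly under the exact one, by procedure group and in total. Tables 10.1 and 10.2 repeat the layout for the cancer-treatment subgroups.

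**The concern.** When vessels within a subject tend to share an outcome, subjects differ from one another more than chance allows. That extra between-subject variation is what makes the Clopper-Pearson interval too narrow, and an adjustment has to capture it. The SAP procedure holds the set of subjects fixed and resamples only inside each one, which treats subjects as fixed strata. A subject with one vessel, or with all vessels in the same category, contributes no variance at all.

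This is the plan's only safeguard for the independence assumption; SAP 8.10 plans no summaries or adjustments by site. The study tests no hypotheses, so estimates and intervals carry its conclusions (SAP section 5: "All estimation of endpoints will be performed using 95% confidence intervals"). Multiple vessels per subject are expected, so the 10% trigger will probably be met. A dependence-adjusted interval that comes out tighter than the unadjusted one invites the wrong conclusion.

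**Working it through.** **Inputs from the SAP.** Vessel-level proportion with Clopper-Pearson (8.4.1); resampling unit, at least 5000 resamples and percentile limits (8.8); 105 to 120 subjects, at least 35 per group (section 1.2). **Assumed, because the documents give no values:** success rate 0.95 (also run at 0.90), vessels per subject (the SAP expects at least one per procedure), within-subject correlation rho, and beta-binomial outcomes.

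**The plan's own figures.** Section 8.8 gives no numerical result. The only computed figures in the plan (section 7) reproduce: 1 − 0.98^105 = 88.0%, and 1 − 0.025^(1/105) = 3.45%, below 3.5%. They do not bear on this point.

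**Algebra.** Subject i has m_i vessels and observed proportion p_i; M is the total number of vessels and p the pooled proportion.

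- SAP bootstrap variance: `sum[m_i p_i(1−p_i)] / M²`
- Binomial variance: `p(1−p)/M = {sum[m_i p_i(1−p_i)] + sum[m_i(p_i−p)²]} / M²`

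The SAP scheme drops the second sum, so it can never exceed the binomial variance, whatever the data.

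**The SAP's six displayed subjects** (19 of 24 successes). The within-subject sum is 0.80 + 0 + 0.75 + 0.80 + 0 + 1.20 = 3.55, so the SE is √(3.55/576) = 0.0785. The binomial SE is √[(19/24)(5/24)/24] = 0.0829. This confirms the inequality but says nothing about size in the trial.

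**Expected behaviour with equal m.**

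- SAP variance: `p(1−p)(1−rho)(m−1)/(mM)`
- True variance: `p(1−p)[1+(m−1)rho]/M`

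With p = 0.95, m = 4 and M = 420, √[p(1−p)/M] = 1.063 points. At rho = 0.3 the SAP width is about 2 × 1.96 × 1.063 × √(0.75 × 0.7) = 3.0 points; the correct width is about 2 × 1.96 × 1.063 × √1.9 = 5.7 points.

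**Simulation, 105 subjects × 4 vessels, p = 0.95** (1500 trials, 1000 resamples each). Mean width in points, with coverage:

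| rho | SAP bootstrap | Whole-subject bootstrap | Clopper-Pearson |
|---|---|---|---|
| 0 | 3.6 (91%) | 4.1 (95%) | 4.4 (95%) |
| 0.1 | 3.4 (86%) | 4.6 (94%) | 4.4 (93%) |
| 0.3 | 3.0 (73%) | 5.6 (94%) | 4.4 (86%) |
| 0.6 | 2.2 (50%) | 6.7 (92%) | 4.3 (77%) |
| 1 | 0 (0%) | 7.9 (89%) | 4.3 (64%) |

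The SAP width fell with rho in every other setting run (35 or 105 subjects, p = 0.90 or 0.95, m = 2 or 4). With vessel counts varying around a mean of 5, separate runs for 105 subjects gave SAP coverage of 90–92%, 80–82%, 72–74% and 56–59% at rho 0, 0.1, 0.2 and 0.4.

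**Just above the trigger** (12 of 105 subjects with two vessels, the rest with one, p = 0.95). The SAP interval averages 1.9 points wide with 35% coverage at rho = 0, and 1.3 points with 23% at rho = 0.3. Clopper-Pearson is 8.7 points wide with 96–97% coverage. Here the failure arises mainly because single-vessel subjects add no variance.

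**Fixed data, 105 × 4 with 20 Grade 4 vessels (95.2%).** Clopper-Pearson is 92.7–97.1% throughout.

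| Pattern of failures | SAP bootstrap | Whole-subject bootstrap |
|---|---|---|
| 20 subjects, 1 each | 93.3–96.9% | 93.3–97.1% |
| 10 subjects, 2 each | 93.8–96.7% | 92.4–97.6% |
| 5 subjects, 4 each | 95.2–95.2% | 90.5–99.0% |

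As the same 20 failures concentrate in fewer subjects, the SAP interval shrinks to a point.

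**The case against.** The algebra is not in dispute. The case against is about weight, evidence and remedy.

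- **Weight.** This is a conditional sensitivity row in a descriptive study with no hypothesis and no performance threshold. The point estimate and the Clopper-Pearson interval do not change, the exact interval is always printed alongside, and Listing 11 gives every vessel, so a correct interval can be computed later. All true. But the row would still be published as an allowance for dependence when it is the reverse.
- **Evidence.** The correlations are assumed, and Clopper-Pearson holds up better than the sensitivity row: with a mean of 3 vessels and 105 subjects it covers about 96%, 93%, 91% and 88% at correlation 0, 0.1, 0.2 and 0.4. Part of the SAP bootstrap's shortfall exists even with no dependence, because its expected variance is then (m−1)/m of the correct value. These points stand. The low coverage figures belong to the bootstrap row, not to the primary interval.
- **Remedy.** Whole-subject resampling does not widen every interval. On the SAP's six illustrative subjects, whose failures are spread out, it gives 69–90% against 62.5–92% under the SAP scheme. With 35 subjects it under-covers (80–87% at p = 0.95 and two vessels each), and it collapses when no vessel is Grade 4. These limits also stand; they are why a companion interval is needed. They do not rescue a scheme that omits the relevant variance.

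**Conclusion.** The concern holds. Text and worked table agree on the resampling unit, and nothing elsewhere in the plan corrects it. That the SAP variance cannot exceed the binomial variance is algebra and needs no assumption. Narrowing as dependence grows refers to positive within-subject correlation, the case the analysis is meant to guard against.

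The size depends on assumed success rate, vessel count and correlation. With 105 subjects, four vessels each, 95% success and correlation 0.3, the nominal 95% interval covers about 73% and is roughly half the width it should be (3.0 against 5.7 points). The damage is confined to the sensitivity interval in Tables 9, 10.1 and 10.2. As written, that analysis works against its stated purpose and should be corrected before it is used.

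**What to change.** Rewrite the bootstrap in SAP 8.8:

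1. Within each procedure group, draw n subjects with replacement from its n subjects, keeping each drawn subject's complete vector.
2. Compute the number of 1's over the number of 1's and 0's across the drawn subjects.
3. Repeat at least 5000 times and take the 2.5th and 97.5th percentiles.
4. For the total, draw subjects within procedure group and pool.
5. Replace the illustrative table with one in which subjects repeat or drop out and their vectors stay intact.

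Because a percentile bootstrap is unreliable with 35 subjects and few Grade 4 vessels, also prespecify a small-sample companion. One option is Clopper-Pearson on the effective sample size (M divided by the design effect), stating how the correlation is estimated when failures are few. If no Grade 4 vessel occurs, Clopper-Pearson on the number of subjects is available; it is equivalent to assuming full dependence. The choice of companion is open; the change of resampling unit is not.

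The cost is SAP wording and a few lines of SAS, with no new data. Under positive dependence the interval will generally be wider, and so slightly less favourable.
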